# Study design

## Overview

The ESCAS study is an exploratory, prospective, randomized-controlled, double-blinded Phase 4 clinical trial designed to assess the efficacy and safety of Cerebrolysin in combination with speech therapy compared to a placebo (saline solution) in combination with speech therapy for the treatment of aphasia following acute ischemic stroke. The study includes two treatment groups: one group receiving Cerebrolysin (N=60) and the other receiving a saline solution as placebo (N=60).

## Sample size

The sample size for the ESCAS study was determined through a power analysis, considering several factors such as the type I error (alpha), type II error (beta), and the expected effect size (ES). The objective of the power analysis was to ensure that the study would have an adequate sample size to detect a statistically significant difference between the Cerebrolysin and placebo groups while minimizing the risks of false positive (type I error) and false negative (type II error) results.

### Assumptions considered in sample size calculations

The sample size calculation was based on the following assumptions:

- Type I error (alpha): The probability of finding a statistically significant treatment effect when there is none. In this study, an alpha level of  $\alpha=0.05$  was chosen, which is a commonly used threshold in clinical research.
- Type II error (beta): The probability of failing to detect a true treatment effect when one exists. In this study, a beta level of  $\beta=0.2$  was chosen, which corresponds to a statistical power of  $(1 - \beta)=0.8$ . This means that there is a  $(1 - \beta)$  probability of detecting a true effect, if present.
- Effect size (ES): The expected magnitude of the difference in treatment outcomes between the Cerebrolysin group and the placebo group. In this study, a medium effect size of ES was assumed, based on prior research and expert opinion.

Based on these assumptions, a power analysis was conducted to determine the necessary sample size for each treatment group. The analysis indicated that a sample size of N participants per group would be required to achieve the desired level of statistical power  $(1 - \beta)$  while maintaining an acceptable type I error rate ( $\alpha$ ).

Therefore, the ESCAS study will enroll a total of at least 2N participants, with at least N participants allocated to the Cerebrolysin group and at least N participants allocated to the placebo group. This sample size will ensure that the study has adequate power to detect a treatment effect of the expected magnitude while minimizing the risks of false positive and false negative results.

## Assumed parameters and resulted sample size

Using G\*Power 3.1.9.7 and assuming a medium effect size  $d=0.5$ , an alpha error of  $\alpha=0.05$  and  $\beta=0.2$ , with an allocation ratio of 1 for Wilcoxon-Mann-Whitney test between two groups, we obtained a sample size of 53 patients per group. In order to provide a margin of error for situations such as patient withdrawal, SAEs or protocol violations, we have decided to recruit 120 patients in total for our study, 60 for each arm.

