## Statistical analysis

For comparing numeric values of paired samples, differential values for each pair of values will be computed. Then, the distribution of those differentials will be compared with the normal distribution, using the Shapiro-Wilk test. If the differentials are normally distributed, we will use a one-sample Student T test (equivalent with the Student T test for paired samples) with null hypothesis  $\mu=0$ . If the differentials are not normally distributed, we will use a Wilcoxon signed-rank test with null hypothesis location=0.

For comparing numeric values of unpaired samples the normality of the values in each sample will be tested using Shapiro-Wilk test. If values from both samples are normally distributed, then variance equality between the samples will be assessed using the Bartlett test.

If the variances are equal, then the differences between the two samples will be assessed using a Student T test for unpaired samples and equal variances. If the variances are not equal, then a Student T test for unpaired samples and unequal variances will be used. In both cases, the null hypothesis will be that mean difference is equal to 0. If values from at least one of the samples are not normally distributed, then a Wilcoxon rank sum with null hypothesis of location difference equal to 0 will be performed.

For comparing ordinal values of paired samples, a Wilcoxon signed-rank test will be used, and for unpaired samples, a Wilcoxon rank-sum test will be used.

For comparing the difference in prevalences of variants of one dichotomous or nominal variable, among the groups of another dichotomous or nominal variable (i.e. testing the association between two dichotomous/nominal variables), the Chi test will be used or, where its assumptions would be violated (mainly due to small number of patients in any group), Fisher exact test will be used.

Where applicable, the two-tail p-value is reported. The type 1 error is assumed to be  $\alpha=0.05$ , and as such, results were considered statistically significant for  $p<0.05$ .

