# Some general functions ----
beautiful.p.value<-function(x){ #beautiful p value, if strictly under 0.001 print as <0.001,
otherwise print as =0.***
  x<-as.numeric(x)
  if(is.na(x))
    return("NA")
```

```
if(is.nan(x))
  return("NaN")
if(x<0.001)
  return("<0.001")
return(paste("",round(x,3),sep=""))
}
test.numeric.unpaired<-function(t1,t2){
  ret<-list()
  ret$sum_nas<-sum(is.na(t1))+sum(is.na(t2))
  t1<-t1[!is.na(t1)]
  t2<-t2[!is.na(t2)]
  if(length(unique(t1))==1)
    ret$shapiro.p.t1<-1
  else
    ret$shapiro.p.t1<-shapiro.test(t1)$p.value
  if(length(unique(t2))==1)
    ret$shapiro.p.t2<-1
  else
    ret$shapiro.p.t2<-shapiro.test(t2)$p.value
  if(ret$shapiro.p.t1<0.05|ret$shapiro.p.t2<0.05){ # if any of them is not normally distributed
    ret$final.test<-"Wilcoxon rank sum"
    ret$p.value<-wilcox.test(t1,t2,paired = F)$p.value
  }else{
    ret$bartlett.p<-bartlett.test(list(t1,t2))$p.value
    if(ret$bartlett.p<0.05){ # unequal distrib
      ret$final.test<-"Student T test for unpaired samples and unequal variances"
      ret$p.value<-t.test(t1,t2,paired = F,var.equal = F)$p.value
    }else{
      ret$final.test<-"Student T test for unpaired samples and equal variances"
      ret$p.value<-t.test(t1,t2,paired = F,var.equal = T)$p.value
    }
  }
  return(ret)
}
test.numeric.paired.2<-function(t1,t2){
  ret<-list()
  if(length(t1)!=length(t2))
    stop("Different lengths!")
  ret$na_vals<-is.na(t1)|is.na(t2)
  t1<-t1[!ret$na_vals]
  t2<-t2[!ret$na_vals]
  ret$shapiro.p.t1<-shapiro.test(t1)$p.value
  ret$shapiro.p.t2<-shapiro.test(t2)$p.value
  if(ret$shapiro.p.t1<0.05|ret$shapiro.p.t2<0.05){ # if any of them is not normally distributed
```

```

ret$final.test<-"Wilcoxon signed rank"
ret$p.value<-wilcox.test(t1,t2,paired = T)$p.value
}else{
ret$final.test<-"Student T test for paired samples"
ret$p.value<-t.test(t1,t2,paired = T)$p.value
}
return(ret)
}
test.numeric.paired.1<-function(tx){ #the same idea, but for when I supply only one group of
values
ret<-list()
ret$na_vals<-is.na(tx)
tx<-tx[!ret$na_vals]
ret$shapiro.p<-shapiro.test(tx)$p.value
if(ret$shapiro.p<0.05){
ret$final.test<-"Wilcoxon signed rank"
ret$p.value<-wilcox.test(tx)$p.value
}else{
ret$final.test<-"Student T test for one sample"
ret$p.value<-t.test(tx)$p.value
}
return(ret)
}
contingency.table.test<-function(t){
if(nrow(t)==2 & ncol(t)==2){
f<-fisher.test(t)
bigtotal<-sum(t)
can_use_chisq<-
(sum(t[1,])*sum(t[,1])/bigtotal>=5) &
(sum(t[1,])*sum(t[,2])/bigtotal>=5) &

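### The 53 per group is reproduced only by a one-sided calculation, but the plan tests two-sided at 0.05; on the same assumptions all 120 patients give about 76% power, not 80%.

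*SAP*

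**What the plan says.** The SAP section on sample size assumptions sets alpha at 0.05 and beta at 0.2, that is, power of 0.80. It concludes: "This sample size will ensure that the study has adequate power to detect a treatment effect of the expected magnitude".

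The section on assumed parameters then gives the calculation. It was done in G*Power 3.1.9.7 with d = 0.5, and "with an allocation ratio of 1 for Wilcoxon-Mann-Whitney test between two groups, we obtained a sample size of 53 patients per group". Recruitment is raised to 60 per arm (120 in total) to cover withdrawals, SAEs and protocol violations. Neither section gives the number of tails or the parent distribution, both of which affect the answer for this test.

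The SAP section Statistical analysis is explicit about tails: "Where applicable, the two-tail p-value is reported". The significance threshold there is p < 0.05. The supplementary R code agrees. The between-group rank test is called as "ret$p.value<-wilcox.test(t1,t2,paired = F)$p.value", and the t tests are called in the same style. No alternative argument is given, so R's two-sided default applies. Nowhere does the SAP announce a one-sided test.

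**The concern.** For a two-sided comparison at 0.05 with d = 0.5 and 80% power, an ordinary t test already needs 64 per group. A rank test with a normal parent needs slightly more. A figure of 53 is too low for that and looks like a one-sided result.

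If so, the type II error in the SAP belongs to a test that will not be run. The step from 53 to 60 would then not be a reserve for losses, because it would not even reach the two-sided requirement. A null result would be read against 80% power that the trial does not have on its own assumptions.

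**Working it through.** **Inputs.** From the two sample size sections: d = 0.5, alpha = 0.05, power 0.80, 1:1 allocation, Wilcoxon-Mann-Whitney test, stated result 53 per group, recruited 60 per group. From the section Statistical analysis and the R code: two-sided testing at 0.05.

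**Method.** Power of the rank test by asymptotic relative efficiency (ARE), with n per group:

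- effective size n' = n × ARE, where ARE = 3/π = 0.955 for a normal parent
- degrees of freedom = 2n' − 2
- noncentrality = d × √(n'/2)
- power from the noncentral t distribution, with the critical value at alpha (one-sided) or alpha/2 (two-sided)

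**Step 1: reproduce the 53.** For n = 53, n' = 53 × 0.955 = 50.61, df = 99.2, and noncentrality = 0.5 × √(50.61/2) = 2.515.

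- One-sided critical value 1.660: power 0.8032. At n = 52 power is 0.7965, so 53 is the smallest n that reaches 80%.
- Two-sided critical value 1.984: power 0.702.

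**Step 2: could another setting give 53?** Smallest n per group for 80% power:

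| Setting | One-sided | Two-sided |
|---|---|---|
| Normal parent (ARE 3/π) | **53** | 67 |
| Logistic parent | 46 | 59 |
| Laplace parent | 34 | 43 |
| Minimum ARE (0.864) | 59 | 74 |
| t test (ARE 1) | 51 | 64 |

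Only one of the ten combinations returns 53, and it is one-sided. No two-sided setting comes within two patients of it.

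**Step 3: the two-sided consequence, normal parent.**

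| n per group | n' | Noncentrality | Critical t | Two-sided power |
|---|---|---|---|---|
| 53 | 50.61 | 2.515 | 1.984 | 0.702 |
| 60 | 57.30 | 2.676 | 1.981 | 0.756 |
| 66 | 63.03 | 2.807 | 1.979 | 0.795 |
| 67 | 63.98 | 2.828 | 1.979 | 0.801 |

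The two-sided requirement is therefore 67 per group, 134 in total, before any allowance for losses. Beta is 1 − 0.702 = 0.298 at 53 per group and 1 − 0.756 = 0.244 at 60.

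**Step 4: detectable effect.** Solving the same formula for d at 80% two-sided power gives d = 0.563 with 53 per group and d = 0.528 with 60.

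**Step 5: check by simulation.** With 20,000 simulated trials per setting and normal data shifted by 0.5 SD, the two-sided rank-sum test rejected in 69.9% at 53 per group and 75.1% at 60. The one-sided test rejected in 80.2% at 53. These agree with the formula.

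**The case against.** **The one-sided setting is inferred.** The SAP does not state the tails, so only the G*Power record can confirm how 53 arose. This stands as a point about wording. It does not rescue the figure, because no two-sided setting tried produces 53.

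**The shortfall at 60 per arm depends on the parent distribution.** With a logistic or Laplace parent, two-sided power at 60 per arm would be 81.2% or 91.6% by formula, above the target. The true distribution of change in the aphasia score is unknown, and the rank test is used only when Shapiro-Wilk rejects normality. This also stands as a qualification. But the SAP invokes neither parent and neither reproduces 53, so they cannot support the published calculation. The minimum-ARE bound goes the other way, with 71.3% at 60 per arm.

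**The test is chosen from the data, so the t test may be run instead.** That branch does somewhat better, at 72.2% with 53 per arm and 77.5% with 60, but it also misses 80%.

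**The trial is exploratory and plans no confirmatory analysis.** With all 60 per arm evaluable the gap is about 4 percentage points (80 − 75.6). No estimate, test or type I error rate changes. This limits the harm. It does not make the stated power right, since the SAP still promises adequate power for the assumed effect.

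**Conclusion.** The concern holds: the sample size statement is wrong as written for the analysis that the same document specifies. The stated 53 per group is a one-sided figure in all but name, and the planned tests are two-sided at 0.05.

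On the SAP's own d = 0.5 and the normal parent that reproduces its number, 80% power needs 67 per group. The trial has 75.6% if all 60 per arm are evaluable and 70.2% if the margin is used up and 53 remain. The conclusion rests on the normal-parent ARE calculation. The t-test branch supports it, whereas a clearly heavier-tailed distribution would bring 60 per arm above 80%. No loss rate is given in the SAP, so power between 53 and 60 evaluable per arm should be read as a range.

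**What to change.** Keep 120 patients and correct the two sample size sections:

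1. Check the G*Power record and state the number of tails and the parent distribution. If the record confirms it, say that 53 per group came from a one-tailed calculation with a normal parent.
2. Replace the claim of 80% power with the two-sided figures at alpha 0.05 and d = 0.5: about 76% with 60 evaluable per arm and about 70% with 53. Note that 67 per arm would be needed for 80%.
3. Give the effects detectable with 80% two-sided power: d = 0.53 with 60 per arm and d = 0.56 with 53.
4. Remove the description of 60 per arm as a margin above the required size, and the statement that the sample size ensures adequate power.

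The cost is a change of SAP wording and a less favourable power statement. No extra patients and no change to the tests or code are needed.

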## Randomisation

Randomisation was discussed at length in the CSP. Briefly, patients meeting inclusion and exclusion criteria will obtain a random number corresponding to the random list generated in advance by a biometrician selected by the Coordinator. Three opaque randomization envelopes will be distributed: to the nurse in charge of preparing the infusion solution, to the study center in case of suspicion of harm to the patient, as well as to the study coordinator.

The study and database will be unblinded after closure of the database and determination of the analysis populations.

## Study schedule

### Visit schedule

- Visit 1 - Day 0 - Baseline, 3-5 days post-stroke
  - Demographics
  - Medical history
  - Western Aphasia Battery
  - NIHSS
- Visit 2 - Day 30  $\pm$  3
  - Western Aphasia Battery
  - NIHSS
  - Barthel Index
  - modified Rankin Scale
  - Adverse Events (AE)
  - Severe Adverse Events (SAE)
- Visit 3 - Day 60  $\pm$  3
  - Western Aphasia Battery
  - NIHSS
  - Barthel Index
  - modified Rankin Scale
  - Adverse Events (AE)
  - Severe Adverse Events (SAE)
- Visit 4 - Day 90  $\pm$  3
  - Western Aphasia Battery

- NIHSS
- Barthel Index
- modified Rankin Scale
- Adverse Events (AE)
- Severe Adverse Events (SAE)

## Treatment schedule

- Treatment Cycle 1 – 30 ml Cerebrolysin/saline and ST for 2 x 5 days (2 weeks)
  - Study days 1 – 14
  - 30ml Cerebrolysin/saline i.v.
  - 1h Speech Therapy
- Treatment Cycle 2 – 30 ml Cerebrolysin/saline and ST for 2 x 5 days (2 weeks)
  - Study days 29-42
  - 30ml Cerebrolysin/saline i.v.
  - 1h Speech Therapy
- Treatment Cycle 3 – 30 ml Cerebrolysin/saline and ST for 2 x 5 days (2 weeks)
  - Study days 57-70
  - 30ml Cerebrolysin/saline i.v.
  - 1h Speech Therapy

## Study endpoints

*The statistical analysis methods selected for the ESCAS study are designed to address the study objectives and provide meaningful insights into the efficacy and safety of Cerebrolysin in the treatment of aphasia after acute ischemic stroke. The chosen methods are tailored to the types of variables included in the study and their distributions. A combination of nonparametric tests, contingency table analyses, and graphical representations will be used to analyze the data.*

*The study endpoints for the ESCAS study are designed to capture the efficacy and safety of Cerebrolysin in combination with speech therapy compared to placebo (saline solution) in combination with speech therapy for the treatment of aphasia following acute ischemic stroke. The endpoints are divided into primary and secondary endpoints, reflecting the prioritization of the study objectives.*

## Primary endpoint

The primary endpoint of the ESCAS study is the comparison of the Western Aphasia Battery (Romanian translated version) scores between the Cerebrolysin and placebo groups at each time point (30, 60, and 90 days after study inclusion) compared to baseline. The Western Aphasia Battery is a standardized assessment tool used to evaluate language function in patients with aphasia. The study will use paired-measurement statistical tests to determine the efficacy of Cerebrolysin in improving language-related outcomes in the study population.

Additionally, unpaired-measurement statistical tests will be used to determine the differences between efficacy of the treatments between groups, at each time point.

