## Secondary endpoints

*By evaluating these primary and secondary endpoints using paired-measurement statistical tests, the ESCAS study will provide a comprehensive assessment of the efficacy and safety of Cerebrolysin in the treatment of aphasia after acute ischemic stroke. This will help to inform clinical decision-making and guide future research in this area*

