## Analysis sets

The statistical analysis will be done separately and will be reported for each of the following study populations. Assessment of inclusion and exclusion will be done independently for each patient and each analysis set. Each patient will be included in all the relevant analysis sets.

Of mention is the fact that the same statistical procedures will be applied to the PP and ITT populations, the difference being in the selection of patients based on subsetting the database.

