## Exploratory statistics

For WAB scores (and their specific subscales) as well as for NIHSS scores, we will calculate the differences between the scores at visits 2/3/4, and their corresponding baseline scores. These differences will be denoted with a lowercase letter "d." Throughout this section, we will refer to these values as *differentials*.

We will assess the normality of the differentials distributions for each group and visit using the Shapiro-Wilk test.

- If the distributions of the differentials show no statistically significant differences compared to the normal distribution, across all groups and visits, then those differentials will be tested against null hypotheses of  $\mu=0$  using one sample Student T test. This would be the equivalent of testing the values of the scores for each group, at visit 2/3/4, against the baseline measurements of each respective group using paired-sample Student T test. Moreover, for each visit, we will compare the differentials between groups using Student T test for unpaired samples and equal or unequal variances, depending on the result of a Bartlett test for variance equality between groups.
- In cases where significant differences exist in the distribution of the differential values for certain groups and visits, compared to the normal distribution, we will test all differentials against the null hypothesis of location=0 using a one-sample Wilcoxon signed-rank test. This approach is equivalent to comparing the values of the scores for each group at visits 2, 3, and 4 against their corresponding baseline measurements using a Wilcoxon signed-rank test. Moreover, for each visit, we will compare the differentials between groups using a Wilcoxon rank-sum test.

For BI and mRS scores, differences from visit 2 to visit 3 and 4 respectively will be assessed in the same way, with paired-sample tests, and differences between groups will be assessed using unpaired-samples tests. .

The number of patients with at least an active AE, SAE and specific AE class, will be reported. Incidence of AEs, SAEs and AE specific classes will be compared between groups using

Chi test or where its assumptions are violated, Fisher's exact test. Moreover, the number of AEs and SAEs for each patient will be compared between groups using Wilcoxon rank-sum tests.

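### The SAP assigns the determination of efficacy to within-arm paired tests against baseline, contradicting its own between-group endpoint, objectives and sample size basis

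*SAP*

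**What the plan says.** The Primary endpoint section opens with a between-group definition: "comparison of the Western Aphasia Battery (Romanian translated version) scores between the Cerebrolysin and placebo groups at each time point", at days 30, 60 and 90 relative to baseline. It then gives the efficacy role to another kind of test: "The study will use paired-measurement statistical tests to determine the efficacy of Cerebrolysin in improving language-related outcomes in the study population". The comparison of the arms comes last: "Additionally, unpaired-measurement statistical tests will be used to determine the differences between efficacy of the treatments between groups, at each time point".

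The lead-in to Secondary endpoints speaks the same way about all endpoints: "By evaluating these primary and secondary endpoints using paired-measurement statistical tests".

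Exploratory statistics shows what the paired tests are. The signed-rank version is described as equivalent to "comparing the values of the scores for each group at visits 2, 3, and 4 against their corresponding baseline measurements", with a null of zero change. The same section then plans a between-group test of the changes at each visit. Planned tables lists both kinds of test, and the R source code runs both.

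On timing, the Visit schedule has "Visit 1 - Day 0 - Baseline, 3-5 days post-stroke". The Treatment schedule gives speech therapy alongside the infusion, whether Cerebrolysin or saline.

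**The concern.** A test of change against zero in one arm makes no use of the control group. Patients enrolled within days of a stroke and given speech therapy can be expected to improve on the Western Aphasia Battery (WAB) with or without the drug. A significant paired result in the Cerebrolysin arm is therefore what one would expect even if the drug did nothing. Yet the two sections quoted name that result as the way efficacy is established.

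There is a second route to error. If the paired test is significant under Cerebrolysin and not under saline, the contrast looks like a treatment effect, although two separate within-arm p-values do not compare the arms.

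At stake is the conclusion on the primary endpoint. The question in both Primary objectives sections is Cerebrolysin versus placebo, and only the between-arm test answers it.

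**Working it through.** **1. Which comparison the SAP is built on**

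| SAP section | Comparison |
|---|---|
| Primary objectives (both places) | Cerebrolysin versus placebo |
| Primary endpoint, first sentence | between groups |
| Assumed parameters and resulted sample size | Wilcoxon-Mann-Whitney, two groups |
| Primary endpoint, efficacy sentence | paired, within arm |
| Secondary endpoints, lead-in | paired |

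The last two rows conflict with the first three.

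**2. The plan's own figure.** Inputs: d = 0.5, alpha 0.05, power 0.80, ratio 1. Take the two-sample noncentral t with relative efficiency 3/π = 0.955 for the rank test.
- Effective n per group = 53 × 0.955 = 50.6; df = 2 × 50.6 − 2 = 99.2; noncentrality = 0.5 × √(50.6/2) = 2.515.
- One-sided power is 0.803, and 53 is the smallest n that reaches 0.80. The stated 53 per group is reproduced.

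So the trial was sized for the between-arm test. The match holds only for a one-sided calculation (two-sided needs 67 per group), which is a separate matter.

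**3. Paired test in the Cerebrolysin arm when the drug does nothing.** Inputs: n = 60 (Sample size), two-sided 0.05 (Statistical analysis). Let r be the mean recovery in SD units of the change, equal in both arms. The SAP gives no value for r, so a range is assumed.

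P(significant) = P(|T| > t), where T is noncentral t with 59 df and noncentrality r√60 = 7.746r, and t = 2.001.

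| Assumed r | Noncentrality | Paired test significant |
|---|---|---|
| 0 | 0 | 5% |
| 0.2 | 1.549 | 33% |
| 0.3 | 2.324 | 63% |
| 0.4 | 3.098 | 86% |
| 0.5 | 3.873 | 97% |
| 0.8 | 6.197 | over 99.9% |

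**4. Significant under Cerebrolysin but not under saline.** The arms are independent, so with p from step 3 the chance is p(1 − p).
- r = 0.2: 0.332 × 0.668 = 0.22
- r = 0.3: 0.628 × 0.372 = 0.23
- r = 0.5: 0.968 × 0.032 = 0.03

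**5. Between-arm test of the same changes.** I simulated 4,000 trials per setting: normal changes, 60 per arm, no drug effect, and the rule in Statistical analysis (Shapiro-Wilk, then Bartlett, then t test or Wilcoxon). The between-arm test was significant in 5.2% at r = 0.2, 4.5% at r = 0.5 and 5.0% at r = 1.0. The paired test in the same runs gave 32%, 97% and 100%, in line with step 3. Equal recovery cancels between the arms.

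**The case against.** The strongest reply is that the right test is already there. It follows in the Primary endpoint section, is specified in Exploratory statistics, is listed in Planned tables, and is printed by the code beside the within-arm p-values. This stands, and it limits the point to the role each test is given. A reader might infer that the plan would ignore the control arm; the documents do not support that.

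A second reply is that the SAP has no success criterion, calls the trial exploratory and plans nothing confirmatory. The lead-in to Secondary endpoints is also loose: it attributes even safety to paired tests, although safety is compared with Chi², Fisher and rank-sum tests. This also stands in part. A reader might infer a false-claim rate near 100%. That would need recovery of about 0.5 SD or more and a claim made on the paired p-value alone, and the SAP fixes neither.

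Neither reply removes the contradiction. No section says that the between-arm result decides efficacy, and two say or imply that the paired result does. A within-arm test answers the wrong question in an exploratory trial as well.

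A reader might also take the three visits and two analysis sets, with none ranked first, as part of the same error. Choosing a lead comparison is a separate matter in a trial with no confirmatory analysis.

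**Conclusion.** The point holds as a contradiction over which test determines efficacy. The efficacy sentence in Primary endpoint and the lead-in to Secondary endpoints point to within-arm paired tests, while the endpoint definition, the objectives and the sizing are all between groups. If those two statements were applied as worded and the drug had no effect, a significant result would arise in 33% of trials at 0.2 SD recovery, rising to over 99.9% at 0.8 SD, against about 5% per visit for the between-arm test.

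The percentages assume equal recovery in both arms, normally distributed changes and 60 evaluable patients in the arm. The recovery sizes are not from the SAP. The conclusion that a within-arm test cannot isolate the drug effect needs only some recovery in both arms, which the early baseline and shared speech therapy make very likely.

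**What to change.** - **Primary endpoint and Secondary endpoints lead-in:** state that efficacy is concluded only from the between-arm comparison of change in WAB Aphasia Quotient, and that within-arm changes are descriptive. Say the same for NIHSS under Efficacy. Align Exploratory statistics and Planned tables.
- **dWABAQ and dNIHSST tables (ITT and PP):** blank the within-arm p-values and test names, which are columns 3 and 4 of rows 4 and 5 in each visit block, or label them as not evidence of efficacy. Keep column 5: it holds the between-arm p-value and test name in those same rows, so the rows must not be deleted. In the code, the assignments to change are those in the branch for scores that are already differentials, which leaves the Barthel Index and Rankin tables untouched.
- **Optional:** name one visit and population as the lead comparison, for example day 90 in ITT. Cycle 3 runs on days 57 to 70, so day 90 is the only visit after all three cycles. This would also mean editing both Primary objectives sections, and possibly the protocol, which is not at hand.

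The first two items cost some rewording and a small code edit. They need no new analysis and no further patients or data, and are best made before unblinding. The sponsor gives up only the option of presenting within-arm p-values as evidence of efficacy.
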